8 STUDY ASSESSMENT AND PROCEDURES

8.1 Efficacy Assessments

User Subject Enrollment: Anesthesiologists (attendings, fellows, residents) and CRNAs who perform airway procedures under general anesthesia will be screened and recruited to the study as described in [Section 5](#) above. The anesthesia attendings work in teams with the residents and CRNAs and therefore, each anesthesia attending user subject will be assigned a unique identifier number and a unique biocontainment device that also has a unique ID number. This information will be collected as part of the device use forms to track the use of each device during the trial. User data to be collected includes first and last name, contact phone number and email address, age, gender, years of experience, healthcare degree, and training level.

User Subject Device Training: User subjects will undergo training on use of the biocontainment device as described in the Device preparation, use cleaning and storage **Section 6.2.4**. This will include in person or video demonstration of device use, review of a written user guide and an opportunity to setup and use a demo unit. Training will also include reviewing reporting any AEs, SAEs, ADEs or UADEs to the PI or qualified designee.

Patient Subject Recruitment: Patients who are undergoing airway procedures under general anesthesia who are assigned to the user subject's usual case-load will be recruited on the day of the procedure for the study. Inclusion and exclusion criteria will be as described above in Section 5. Recruitment will take place on the day of the procedure as cases and assigned providers can shift at the last minute and this will help ensure enrollment efficiency for patient subjects in the study. The on-site participation of the patient in the trial is limited to the actual scheduled procedure that includes an airway procedure under general anesthesia.

Airway procedure and patient data collection: Patient data and data from the anesthesia data record will be collected by PIs or their qualified designee post-airway procedure. As a result of social distancing and minimizing personnel due to COVID-19, it may not be possible to have a member of the research team present to observe and record data from each procedure. The airway procedures will be recorded using a GoPro camera placed in a fixed position. Data from the memory card will be transferred to an institutionally secured and managed network drive. Device use data will be collected from the videos by the PI or qualified designee. This data will include length of time to setup the device, length of time to perform the airway procedure, length of time to remove the device, number of times hand ports were used per procedure, and positioning of the torso drape. Patient data collected from the medical record will include patient demographics, contact information (phone and email), age, gender, race, co-morbid conditions (i.e. cardiac disease, lung disease, diabetes, BMI), smoking status. Airway procedure-related data that will also be collected will include BMI, hyomental distance, Mallampati score, type of airway procedure performed, number of attempts to perform the airway procedure, devices used for airway procedure, use of mask ventilation, anesthesia sequence used, and experience level of person performing the airway procedure.

Quality Use Survey and Safety Data Collection: As part of the study, user subjects will complete a Quality Use Survey after each day using the device. The results of the survey will be transferred from hard copies or REDCap to electronic format in CTMS for storage. This survey will collect user information on device functionality, perceived benefit of device use, healthcare burden associated with the device and safety data associated with device use. Safety data collected will include: 1) injury to the patient subject (patient in ABCD) or user subject (healthcare provider), 2) healthcare provider perceived patient subject anxiety or claustrophobia, 3) difficulty performing intubation with or without requiring removal of the device, 4) observed device defects or failures (i.e. broken strap, crack in plexiglass, break in hand ports).

Patient Subject Experience Survey: The patient subject's randomized to device use will be asked in the recovery room post-procedure or receive a phone call or email with REDCap survey link from a qualified study coordinator to answer a short patient experience survey where the data will be collected in REDCap and subsequently transcribed into CTMS. Data collected will include: 1) overall comfort in the device, 2) sensation of increased anxiety, 3) sensation of claustrophobia, 4) perceived safety in the device, 5) any difficulties seeing or hearing while in the device, 6) any additional comments or suggestions regarding the experience in the device. All data will be collected on a Likert scale and stored in CTMS.

Patient subjects' medical records medical will be accessed as part of the study. Personal and medical data collected as part of the study will be stored in a de-identified fashion on an institutionally secured and managed network drive and/or computer.

As part of this study, user subjects' medical records will NOT be accessed. Personal data including age, and gender, will be collected as part of the initial data collection instrument and stored in de-identified fashion on an institutionally secured and managed network drive and/or computer.

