3. ASA I, II, III
4. Undergoing planned procedure involving an airway procedure under general anesthesia
5. Age 18 years or older

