8.3.2 Classification of an Adverse Event

8.3.2.1 Severity of Event

Adverse events will be classified based on the defined grading system:

- Mild: events require minimal or no treatment and do not interfere with the participant's daily activities
- Moderate: events result in low level of inconvenience or cause some inference with functioning
- Severe: events interrupt a participant's usual daily activity. Severe events are usually potentially life-threatening or incapacitating. Please note, the term "severe" does not necessarily equate to "serious".

8.3.2.2 *Relationship to Study Intervention*

All adverse events (AEs) and ADEs must have their relationship to the study device assessed by the PI who examines and evaluates the participant based on temporal relationship and his/her clinical judgment. The degree of certainty about causality will be graded using the categories below. In a clinical trial, the study product must always be considered.

- Definitely Related – The AE/ADE is known to occur with the device.
- Probably Related – There is a reasonable possibility that the device caused the AE, or there is a temporal relationship between the device use and event. Reasonable possibility means that there is evidence to suggest a causal relationship between the device and the AE/ADE.
- Possibly Related - There is a possibility that the device caused the AE, or there is a temporal relationship between the device use and event. There is no evidence to suggest a causal relationship between the device and the AE/ADE but an alternate etiology has not yet been established.
- Unrelated – There is not a reasonable possibility that the use of the device caused the event, there is no temporal relationship between the use of the device and event onset, or an alternate etiology has been established.

8.3.2.3 *Expectedness*

Expected adverse events associated with this study that will be tracked and reported include:

1. Minor injury to the patient subject or provider
2. Patient claustrophobia
3. Patient anxiety
4. Difficulty performing intubation with the device in place
5. Need to remove the biocontainment device to safely perform intubation

Potential SAEs associated with this study would include:

1. Major physical injury to patient or provider due to device failure.

A UADE for this device would be breakdown or malfunction of the device during use.

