9.4 Statistical Analyses

9.4.1 General Approach

Descriptive statistics:

- The number of subjects who utilized the protective device will be included; the level of experience and training of user subjects will be included.
- Patient subject baseline demographics, co-morbidities, smoking status, and intubation-related factors will be included.
- Objective data regarding total time for the airway procedure, number of intubation/LMA/extubation attempts, airway device used (i.e. intubation blade used and size of ETT) will be included.
- The user subjects comfort level for device use will be graded on a continuous scale, and the mean comfort level calculated as well as the range.
- The patient subjects comfort level and experience in the device will be graded on a continuous scale, and the mean comfort/experience level calculated as well as the range.
- Categories for various healthcare burdens will be provided as options for participants; the mean for most common burden will be identified; the percentage for each burden subtype will also be identified.

Inferential Tests

- A p-value of 0.05 and 95% confidence interval will be utilized when determining if the protective device results in an improvement in outcomes measures, i.e. a decrease in the number of COVID-19 cases by participants.
- Chi-square testing or ANOVA will be used.

Covariates will be collected on participants, including but not limited to subspecialty training, years of experience as a resident, fellow, or attending, as well as gender.

Assumption of normality of data points will be determined using Q-Q plots. If there are limitations to performing assumptions of normality, then appropriate non-parametric corrections would be performed.

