9.4.2 Analysis of the Primary Efficacy Endpoint(s)

Primary Endpoints:

1. Assessment of time to complete an airway procedure with or without the biocontainment device. The time is measured as a single quantitative measure at the end of the procedure. The initial starting time (T0) is defined as “time the mask is removed from the patient just prior to initiation of the airway procedure”. End time (T1) is defined as the time that the airway procedure is completed with a secure airway defined as the

time the airway device is secured to the airway circuit. Data will be presented as median amount of time for a given procedure with or without the biocontainment device and statistical significance will be determined by analysis of variance (ANOVA). Additionally, a multiple regression model will be created using covariates of subject user experience, number of prior uses with the device, and patient specific factors (co-morbid conditions, BMI, Mallampati score). This will help determine the critical factors associated with time to use the device.

2. The total number of AEs and ADEs will be presented. This will be broken down by specific AE or ADE. Logistic regression will be used to assess possible contributing factors to AEs or ADEs including subject user experience, airway procedure performed, patient-specific factors (BMI, co-morbid conditions, Mallampati score). We anticipate a low number of AEs/ADEs and as such, statistically rigorous regression analyses may be limited by a low overall number of events.

Statistical analyses will be performed on all data points, however, a sub-analysis will be performed on participants without any missing data points.

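### Difficulty and device removal are worded for intubation although any airway procedure is enrolled and timed, so these events may be under-reported for LMA placement

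*Combined protocol and SAP*

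**What the plan says.** **Scope of the trial.** The inclusion criterion in section 5.1 is "Undergoing planned procedure involving an airway procedure under general anesthesia". Section 6.2.4 leaves the airway technique to the attending anesthesiologist. The first primary endpoint in 9.4.2 is "Assessment of time to complete an airway procedure with or without the biocontainment device", and its clock stops when the airway device is connected to the circuit, which fits an LMA as well as a tube. Section 8.1 collects the type of airway procedure, and 9.4.1 summarises the "number of intubation/LMA/extubation attempts".

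**Safety items.** The Quality Use Survey item in 8.1 is "difficulty performing intubation with or without requiring removal of the device", and 2.2.2 item 4 has the same wording. The expected events in 8.3.2.3 include item 4, "Difficulty performing intubation with the device in place", and item 5, "Need to remove the biocontainment device to safely perform intubation".

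**Analysis.** The number of AEs and ADEs is the second primary endpoint. Section 9.4.2 states: "Logistic regression will be used to assess possible contributing factors to AEs or ADEs including subject user experience, airway procedure performed". It adds that few events are anticipated and that the regression may be limited for that reason.

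**The concern.** The set of procedures that is timed and modelled is wider than the set for which difficulty and device removal are described. A user who struggled to place an LMA, or took the box off to do so, could reasonably answer the survey item in the negative because no intubation was attempted.

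If that happens, ascertainment of part of a co-primary endpoint depends on procedure type, which is itself a planned covariate in the model for that endpoint. Two results could be affected. The AE/ADE count may be understated, and the procedure-type coefficient may suggest that the device causes fewer problems with LMA when the difference lies partly in what was asked. The interim check in 9.4.5 looks at the trend in the same count, so it could also move with case mix.

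**Working it through.** The documents give no LMA share, AE rate or AE-model figure, so there is no planned number to reproduce. The check has two parts.

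**1. Wording side by side**

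| Element | Section | Covers |
|---|---|---|
| Eligibility | 5.1 | any airway procedure |
| Procedure time | 9.4.2 | any airway procedure |
| Number of attempts | 8.1, 9.4.1 | any airway procedure; LMA named in 9.4.1 |
| AE regression covariate | 9.4.2 | type of airway procedure |
| Anticipated AE, item 4 | 2.2.2 | intubation |
| Survey safety item 3 | 8.1 | intubation |
| Expected AEs, items 4 and 5 | 8.3.2.3 | intubation |

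Difficulty and removal are worded for intubation in every list of tracked safety items. The other listed patient and user events (injury, anxiety, claustrophobia) are not tied to a procedure type.

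**2. Size under stated assumptions**

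Inputs:
- Device procedures: 100 (section 1.3).
- LMA share *q*: assumed 0.10 to 0.50.
- True rate of difficulty or removal *d*: assumed 0.05 to 0.20, equal for LMA and intubation.
- Rate of other AEs *b*: assumed 0.05 to 0.15, independent of difficulty and always captured.
- Share *r* of LMA difficulty events captured by other routes: 0 for the literal reading, then varied.

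Formulas:
- Probability of any AE when fully captured: *p* = 1 − (1 − *d*)(1 − *b*).
- Procedures with any AE: true 100*p*; captured at *r* = 0, 100[(1 − *q*)*p* + *q b*].
- Apparent odds ratio, LMA versus intubation, at *r* = 0: [*b*/(1 − *b*)] / [*p*/(1 − *p*)]. The true value is 1.

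Worked case, *q* = 0.3, *d* = 0.10, *b* = 0.05:
- Difficulty events captured: 100 × 0.7 × 0.10 = 7 of 10.
- *p* = 1 − 0.90 × 0.95 = 0.145, so 14.5 procedures truly have an AE.
- Captured: 14.5 − 30 × (0.145 − 0.05) = 11.65, a loss of about 20%.
- Odds ratio: (0.05/0.95)/(0.145/0.855) = 0.31.

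This case and the two ends of the range:

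| *q* | *d* | *b* | True | Captured | Lost | Odds ratio |
|---|---|---|---|---|---|---|
| 0.1 | 0.05 | 0.15 | 19.2 | 18.8 | 2.2% | 0.74 |
| 0.3 | 0.10 | 0.05 | 14.5 | 11.7 | 19.7% | 0.31 |
| 0.5 | 0.20 | 0.05 | 24.0 | 14.5 | 39.6% | 0.17 |

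Counting events rather than procedures, with at most one event of each kind per procedure, the share lost is *q d*/(*d* + *b*): 2.5%, 20% and 40% in the same three rows.

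Partial capture, with *d* = 0.10 and *b* = 0.05: the LMA probability becomes 1 − (1 − *r d*)(1 − *b*), and the odds ratio is 0.64 at *r* = 0.5, 0.92 at *r* = 0.9 and 1.00 at *r* = 1. With *q* = 0 nothing is lost.

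**The case against.** The strongest reply is that *intubation* is shorthand here for the study procedure. Sections 1.3, 4.1 and 6.3 describe all patients as randomized to intubation with or without the device, and the same loose reading is available for the safety items. AE capture is also wider than the survey item. The AE/ADE definition in 8.3.1.1 is not limited by procedure, 8.3.3 provides for open questioning and volunteered reports, and 7.1 treats inability to complete any airway procedure with the device as discontinuation of device use. Attempts and device-removal time are recorded for every procedure. Section 8.3.2.3 sorts events by expectedness, so an unlisted event is still an AE. The survey form itself is not in the documents; 8.1 only describes its content.

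Much of this stands. It rules out the stronger reading that a reader might infer, namely that LMA difficulty is not collected, that the AE count is therefore too low, and that any procedure effect is an artefact. No text excludes LMA events. Nor would the AE model necessarily break down. A table such as 7/70 versus 0/30 for difficulty alone has an infinite odds ratio, but that needs zero capture by every route and leaves out the other AE types. Even that table gives a Fisher p of only 0.10. The documents also give no event frequencies, so these cannot be called the commonest device effects.

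The reply does not remove the point. Section 9.4.1 lists intubation and LMA as different things, and 8.1 moves from the general term for timing and attempts to the narrow one for safety. Difficulty without harm is not clearly an untoward medical occurrence under 8.3.1.1; its place on the lists is what makes it a tracked event. Attempt counts and removal times do not record why the device came off. Later recovery is also uncertain: 8.1 accepts that research staff may be absent (8.2 says otherwise), and videos are deleted within 14 days (10.1.4, 10.1.8.1).

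**Conclusion.** The point holds as a conditional one and should be corrected. The wording mismatch is plain in the text. Whether it biases anything depends on how users read the item and on how many non-intubation procedures are enrolled, and the documents settle neither. If the item is read literally, the co-primary AE/ADE count may be understated and the procedure-type coefficient may be biased toward fewer AEs with LMA.

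Under the assumed ranges and zero capture by other routes, about 2-40% of procedures with an AE would be missed, and a true null would appear as an odds ratio of 0.17-0.74. These figures assume equal true difficulty across procedure types. They show sensitivity and do not predict the result. The bias shrinks to nil as other routes capture the events or as the LMA share goes to zero. A procedure effect would be mixed with ascertainment, not wholly produced by it, because only the difficulty and removal terms are affected.

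**What to change.** Replace *intubation* with *the airway procedure* in 2.2.2 item 4, in Quality Use Survey safety item 3 in 8.1 (and on the form, if it follows that wording), and in 8.3.2.3 items 4 and 5. In 9.4.2, report difficulty and device-removal counts by procedure type, with the number of device procedures of each type as denominator.

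The cost is one survey item and three list entries reworded. Procedure type is already collected, so no new data field is needed, and clinical management does not change. The AE count may become slightly less favourable to the device.

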1 STUDY SUMMARY

1.1 Synopsis

Title: Aerosol Biocontainment Device (ABCD) with Aerosol Clearance for Aerosol Generating Procedures

Short Title: Aerosol BioContainment Device (ABCD)

Study Description: The primary goal of this study is to assess use of a biocontainment device for planned airway procedures under general anesthesia. This will serve as a platform for using this device as a novel biocontainment and aerosol evacuation system as part of rapid sequence intubation protocols for COVID-19 patients. We hypothesize that airway procedures with the aerosol biocontainment device will be safe and effective with airway procedure times approaching times for airway procedures without the device.

Objectives: The primary objectives of this study are: 1) Assess changes in airway procedure time with and without the biocontainment device as a function of repeated utilization and as a function of patient-associated airway factors (i.e. Mallampati score, hyomental distance, neck mobility, BMI) and user-associated airway factors (i.e. experience of user, airway device used, induction sequence) 2) Assess adverse events, adverse device events associated with biocontainment device use.

Secondary objectives include: 1) Assess the subject's comfort with using the biocontainment device. 2) Assess for additional healthcare and cognitive burden imposed by the device. 3) Survey of patient's post-procedure on experience being inside the device. Exploratory objectives include gathering specific feedback regarding possible design modifications for further iterations and design improvements with the engineering team.

Primary Endpoint: The primary endpoints of this study are:
1. Measuring the time for performing an airway procedure with the biocontainment device when accounting for patient and user-specific factors.
2. Quantifying the number of AEs or ADEs over time to assess device safety.

Secondary Endpoints: The secondary endpoints include:
1. Median Likert ratings from device use survey questions that assess user subject device comfort.
2. Median Likert ratings from device use survey questions that assess user subject healthcare burden with the device.
3. Median Likert rating of the patient questionnaire results to assess patient experience in the device.

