8.3.3 Time Period and Frequency for Event Assessment and Follow-Up

Safety will be assessed by monitoring and recording potential adverse effects using the quality use survey and the patient survey questionnaire as defined in [Section 1.3](#). Participants will be monitored by these questionnaires. Any adverse events/ADEs are captured and shared with study PIs and the Sponsor. AEs and SAEs will be assessed for daily and completeness of surveys (data integrity) will be assessed weekly.

The investigator will seek information on adverse events by non-directive questioning. Adverse events may also be detected when they are volunteered by the clinician utilizing the device. Information on all adverse events will be recorded in the source documentation. To the extent possible, adverse events will be recorded as a diagnosis and symptoms used to make the diagnosis recorded within the diagnosis event.

As much as possible, each adverse event or follow-up information will be evaluated to determine:

1. Severity grade (as described in [Section 8.3.2.1](#) above)
2. Duration (start and end dates)
3. Relationship to the study treatment or process – (As described in [Section 8.3.2.2](#) above)
4. Expectedness to study treatment or process – [Unexpected – if the event severity and/or frequency is not described in the investigator brochure (if applicable) or protocol].
5. Action taken with respect to investigational device or process (none, permanently discontinued, unknown, not applicable)
6. Whether the event is serious

Once an adverse event is detected, it should be followed until its resolution or until it is judged to be permanent, and assessment should be made weekly (or more frequently, if necessary) of any changes in severity, the suspected relationship to the study treatment, the interventions required to treat it, and the outcome.

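### The patient survey is a named safety instrument, but its listed topics omit injury and no rule says when an anxiety or claustrophobia rating becomes an AE, so events patients notice later may be under-captured

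*Combined protocol and SAP*

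**What the plan says.** The second primary endpoint in the Synopsis (1.1) is a count: "Quantifying the number of AEs or ADEs over time to assess device safety". Section 9.4.2 presents the total and breaks it down by type of event.

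For capture, section 8.3.3 relies on "monitoring and recording potential adverse effects using the quality use survey and the patient survey questionnaire". It adds non-directive questioning by the investigator and events volunteered by the clinician using the device. Section 8.3.4 runs AE reporting from consent to the end of the study.

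The expected AEs in section 8.3.2.3 begin with "Minor injury to the patient subject or provider" and include patient claustrophobia and patient anxiety.

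Section 8.1 gives the content of both instruments:

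- **Quality Use Survey.** It states that "user subjects will complete a Quality Use Survey after each day using the device". Its safety items include injury to the patient and anxiety or claustrophobia as perceived by the provider.
- **Patient survey.** It opens with "Data collected will include: 1) overall comfort in the device, 2) sensation of increased anxiety, 3) sensation of claustrophobia" and continues with "4) perceived safety in the device, 5) any difficulties seeing or hearing while in the device, 6) any additional comments or suggestions". On format: "All data will be collected on a Likert scale and stored in CTMS". It goes only to patients randomized to the device. They may be asked in the recovery room, by phone or by an emailed link, with a 1-week target (1.3).

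Section 9.4.3 analyses the patient survey only as ordinal data for secondary endpoint 3.

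**The concern.** One of the two instruments that carry the safety assessment is not described as asking about the first event on the expected list. For the two expected events it does cover, it yields an ordinal rating, while the endpoint needs a number of events.

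The injury item that does exist is answered by the user on the day. The patient is under general anesthesia for the airway procedure, and section 6.2.4 has the device slid out from beneath a sedated patient's head. Soreness or a bruise could become apparent only after the user's form is complete. For anxiety and claustrophobia the patient is the more direct source, yet only the provider's perception sits among the items labelled as safety data.

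The AE/ADE count is a primary endpoint, the outcome of the logistic regression in 9.4.2, and the quantity whose upward trend would pause the study under 9.4.5. If capture is incomplete, or depends on who judges a rating to be an event, all three uses inherit the problem.

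**Working it through.** The plan states no figure on this point, so there is nothing to reproduce. The check sets the capture routes side by side and then illustrates the effect of incomplete capture.

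**Step 1. Routes by which a patient event could enter the count**

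| Route | Section | Injury noticed after the day of use | Patient-felt anxiety or claustrophobia |
|---|---|---|---|
| Quality Use Survey | 8.1 | Asked of the user, but the form is completed that day | Provider's perception only |
| Patient survey, topics 1 to 5 | 8.1 | Not a listed topic | Rated, with no event rule |
| Patient survey, comments | 8.1 | Possible if the patient raises it | Possible if the patient raises it |
| Investigator questioning | 8.3.3 | Possible, no time point given | Possible, no time point given |
| Volunteered by clinician | 8.3.3 | Only if the clinician learns of it | Only if the clinician learns of it |
| Medical record | 8.1 | Listed fields are baseline and airway data | Same |

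The Schedule of Activities (12.1) has an AE/ADE review row, placed in the airway-procedure column. It does not say when a patient is asked. The survey is the only patient contact it shows after the procedure, and 8.1 limits the patient's on-site participation to the procedure itself. The comments item is also nominally Likert-scored, which does not suit free text.

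**Step 2. From rating to event**

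The AE definition in 8.3.1.1 is broad and includes investigator judgement. It sets no rating level. Sections 8.3.3, 9.4.2 and 9.4.3 supply none either. Two assessors could therefore read the same ratings and report different counts.

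**Step 3. Illustration of incomplete injury capture**

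Input from the plan: 100 device procedures (1.3). Assumed, because the documents give neither: true injury rate r and the proportion s of injuries captured by all routes together.

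Expected recorded injuries = 100 × r × s. Chance of recording none = (1 − r × s)^100.

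| r | s = 1 | s = 0.75 | s = 0.5 | s = 0.25 |
|---|---|---|---|---|
| 1% | 36.6% | 47.1% | 60.6% | 77.9% |
| 2% | 13.3% | 22.1% | 36.6% | 60.6% |
| 3% | 4.8% | 10.3% | 22.1% | 47.1% |
| 5% | 0.6% | 2.2% | 8.0% | 28.4% |

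Worked case, r = 2%: with full capture, 0.98^100 = 0.133, with 2 injuries expected. With half captured, 0.99^100 = 0.366, with 1 expected.

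**The case against.** The strongest reply is that the plan has other routes. Investigator questioning, a reporting period that runs to the end of the study, and a comments item all leave room for a later bruise to be recorded. A reader might infer that injuries noticed after recovery are missed. The documents do not support that. They support only that no structured or timed enquiry is made of the patient.

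A reader might also infer that the survey cannot supply AE counts, or that anxiety and claustrophobia events will be produced by cutting the ratings after unblinded data are seen. Neither follows. A rating or comment could prompt an AE assessment by the investigator, the user's form gives a second source for both events, and nowhere does the plan propose to cut ratings into events. What is missing is the trigger rule.

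Two further points have weight. The questionnaire itself is not in the documents, so what can be shown is that injury is not a listed topic. And section 2.3.3 ties abrasion or contusion to a patient sitting up inside the device, which it calls unlikely. The user is well placed to see that, so the case for later discovery rests more on device removal and other contact.

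Finally, the rates in the illustration are all assumed. These replies limit the claim to possible under-capture. They do not close the gap, because the questioning has no time point and only the clinician is named as volunteering events.

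**Conclusion.** The point holds as a gap in capture for a primary endpoint. The patient survey is named as a safety instrument, its listed topics leave out injury, and no rule links its anxiety and claustrophobia ratings to AEs. Injuries that a patient notices after the user's end-of-day form may be under-counted, and the patient-reported contribution to the anxiety and claustrophobia counts cannot be reproduced from the text.

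The size is unknown. The shift from 13% to 37% in the chance of recording no injury rests on an assumed 2% rate and on half of injuries being captured across all routes. If the other routes work well, the loss is small. The documents do not establish that the device will look safer than it is.

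**What to change.** Add three items to the existing patient survey:

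1. Yes/no with free text: any injury, soreness, mark or bruise since the procedure.
2. Yes/no: an episode of anxiety while in the device.
3. Yes/no: an episode of claustrophobia while in the device.

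State in 8.3.3 and 9.4.2 that a yes triggers AE assessment under the definitions in 8.3.1, and that the Likert ratings serve only secondary endpoint 3. For patients who answer in the recovery room, send the injury item by the phone or email route already planned, within the 1-week window. Otherwise it would still not reach what appears later.

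The cost is three short questions, one extra contact for patients surveyed in recovery, and a line in each of two sections. The reported AE count will probably rise and include minor events unrelated to the device. Because only the device arm receives the survey, events solicited this way must be reported as device-arm data and not compared with the control arm.
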